[name]
[contact]
Email: [contact]

[name]
Statistician
Office of Clinical and Regulatory Affairs
National Center for Complementary and Integrative Health (NCCIH)
[name]
Email: [contact]

PRÉCIS

Study Title

Spinal Manipulation and Patient Self-Management for Preventing Acute to Chronic Back Pain (PACBACK)

Objectives

Primary Objective

Our long-term objective is to reduce overall lower back pain (LBP) burden by testing scalable first-line non-pharmacologic strategies that address the biopsychosocial aspects of acute/sub-acute LBP and prevent transition to chronic LBP (cLBP). We will assess the effectiveness of Spinal Manipulation Therapy (SMT), Supported Self-Management (SSM), and SMT+SSM relative to Medical Care (MC).

Secondary Objective

To facilitate translation and dissemination across health professions and other clinical settings we will gather contextual data using mixed methods guided by the Reach, Effectiveness, Adoption, Implementation, and Maintenance (RE- AIM) framework. Qualitative data will lend context regarding patients', staff, providers' and health system leaders' perceptions of barriers and facilitators associated with the interventions; quantitative data collection will provide insight into intervention application, adherence, fidelity, and provider confidence.

Design and Outcomes

This is multi-site, predominantly pragmatic, phase III randomized trial using a 2x2 factorial design. Participants will be randomized to one of the following treatment groups: (1) SMT, (2) SSM, (3) the combination of SMT+SSM, or (4) MC. Physical therapists (PTs) and chiropractors (DCs) will deliver SMT and SSM, and medical providers will deliver the MC. The study has 2 primary effectiveness research questions with different time frames:

1. Prevention of cLBP at 12 months as measured by LBP Impact (from Promis-29) scale: 8-50 (Analysis of AUC for months 10-12)
2. Average pain intensity and low back disability over 1 year as measured by weekly NRS and monthly RMDQ scores.

Secondary outcome measures include: recovery, NIH minimal dataset including the Patient Reported Outcome Measurement Information System-29 (PROMIS-29) and other measures of LBP burden (e.g., productivity loss, health care and medication use, including opioids).

Interventions and Duration

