3.7 Enrollment period and follow-up

Participant enrollment will take approximately 4 months for the UG3 planning and pilot phase and approximately 4-5 years for the main UH3 phase of the trial. Individual participants will be followed on a weekly basis for 52 weeks from randomization.

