6.2.4 Follow-up Visits

Intervention Visits

The following information will be collected at each intervention visit, which will occur as needed throughout the one year as there is no set schedule of treatments:

- Treatment delivery format – in-person, videoconference or phone
- Treatment administered – provider's record treatment administered including required, allowed and prohibited treatments to assess treatment fidelity and adherence. (Clinical notes will be documented in the medical record as required for patient management and for compliance with provider licensing requirements).
- Adverse events (AEs) - participants will be asked about the occurrence of AE/SAEs by their treatment provider at each visit. The AE protocol described in section 7, Safety and Assessments will be initiated and adhered to for all AEs identified.

Weekly Follow-up

Weekly outcomes will be collected electronically via direct patient self-report; participants who are unable to provide electronic data will be contacted directly by blinded study staff who will ascertain outcomes. Additional information related to data collection and quality assurance is described in section 10.

The following outcomes will be collected on a weekly basis for one year (\pm 2 days):

- Primary outcomes
 - Pain intensity
- Secondary outcomes
 - LBP frequency

Monthly Follow-up

Monthly follow-up data (Months 1-12) will be collected electronically via direct patient self-report. Participants who are unable to provide electronic data will be contacted directly by blinded study staff who will ascertain outcomes, or they will be mailed a paper copy of the questionnaire to complete and return to the study team. Additional information related to data collection and quality assurance is described in section 10.

The following outcomes will be collected on a monthly basis for one year (\pm 7 days):

- Primary outcomes
 - Disability - Roland Morris Disability Questionnaire
 - Low Back Pain Impact - subset of PROMIS-29
- Secondary outcomes
 - PROMIS measures, additional healthcare use, medication use, and productivity loss
 - AEs -participants will be queried about AEs associated with study interventions (e.g., increased pain, neurological symptoms, medication side effects etc.).^{11 142}
¹⁴³ The AE protocol described in section 7, Safety and Assessments will be initiated and adhered to for all AEs identified.

Week 2 Follow-up

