Power and Sample Size for the Recovery Outcome: In order to determine the necessary sample size for effectiveness evaluation we need to formulate assumptions for the primary outcome rate in the treatment and control groups. [name] et al.¹¹ compared SMT plus Home Exercise with Advice (HEA) to HEA alone among subacute and chronic patients and find complete recovery from leg pain in 20% of SMT+HEA versus 5% of HEA at 12 weeks, and 23% versus 12.5% respectively at one year (RR=1.84) providing evidence that relative risks in the range of 1.5-2.0 are plausible. The recovery rate at 6 months was estimated based on studies by Kamper et al.¹⁵² and members of our investigative team,¹⁵³ which used the same strict definition for recovery. Kamper et al.¹⁵² summarize recovery rates and criteria based on both NRS and RMDQ from four studies with acute and subacute subjects. Recovery rates range from 7% to 12%. A recent study by [name] et al.¹⁵³ reported a 5% recovery rate within a mixed population of sub-acute and

chronic patients with increased risk for cLBP. Given the potential uncertainty in the recovery rate for the MC group, we varied the expected recovery rate from 5-15% and determined the magnitude of treatment effects for which we have $\geq 80\%$ power.

For simulations we considered crude analysis while our formal analysis will additionally adjust for site and baseline risk yielding improved power since these are variables that only predict outcome and are not related to treatment group. For each scenario we simulated 5,000 data sets and empirically calculated power as the percentage of replicates in which the null hypothesis was rejected.

Figure 9.2 shows the power to test each intervention marginally. We see that we have >80% power to detect a relative risk of 1.75 associated with either SMT or SSM if the UMC recovery rate is 10%. If the UMC recovery rate is 5% then we have power to detect a 5.5% risk difference (RR=2.1), while if the UMC recovery rate is 15% then we have power to detect an 8.3% risk difference (RR=1.55). These effects are also medium in size and considered clinically important by Cochrane's Back Review Group.¹⁴⁸

Primary Effectiveness Outcome # 2 and 3: Determine the effectiveness of SMT, SSM, and the combination of SMT+SSM relative to medical care (MC) in achieving improvements in average pain intensity and back-specific functioning cumulative through 1 year based on monthly measures of RMDQ and weekly Pain NRS scores.

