Effectiveness Hypothesis: We will focus on parallel analyses for pain and function. We hypothesize that SMT alone will decrease average pain by at least 1 point, and average disability by 2 points. Similarly, SSM alone will decrease average pain by at least 1 point, and average disability by 2 points, and the combination of SMT+SSM will lead to an sub-additive net decrease of <2 points and <4 points respectively.

Primary outcome variables: We will derive measure of disability and pain by calculating the time-averaged patient outcome using the monthly measurements taken over the year of follow-up.

Primary Analysis: For quantitative outcomes we will focus on analyses that generally do not assume that the effects of SMT and SSM are additive since we have adequate power to evaluate specific group contrasts. We will use linear regression methods with robust standard errors to test for the difference in mean scores comparing each intervention group to MC. Let Y_{ij} denote the outcome of interest (either average pain or average disability for parallel analyses). Similar to our primary analysis of LBP impact 1 we will use a linear regression model with robust standard errors using the structure:

$$\text{Four Groups Model: } E(Y_{ij} | X_{ij}) = \beta_0 + \beta_1 \cdot \text{Site}(2)_j + \beta_2 \cdot \text{RiskGroup}_{ij} + \beta_3 \cdot \text{SMT-Only}_{ij} + \beta_4 \cdot \text{SSM-Only}_{ij} + \beta_5 \cdot \text{SMT-and-SSM}_{ij} + \beta_6 \cdot \text{Period}(2)_{ij} + \beta_7 \cdot \text{Period}(3)_{ij}$$

In the primary regression model the parameters of interest are:

β_3 = adjusted mean difference comparing SMT Only to UMC;

β_4 = adjusted mean difference comparing SMT Only to UMC;

β_5 = adjusted mean difference comparing combined SMT and SSM to UMC.

This model considers each treatment group separately using an indicator of SMT only (*SMT-Only*), an indicator of SSM only (*SSM-Only*), and an indicator of combined therapy with both SMT and SSM (*SMT-and-SSM*). We will also add the baseline outcome as a covariate to perform a variation of ANCOVA for repeated measures.

Table 9.2: Power for the overall F-test of equality of means under various alternative scenarios.

Average pain intensity & disability over 12 months post-randomization (alpha = 0.05/2)

Alternative	SMT Alone	SSM Alone	SMT + SSM	Power
Additive	0.20	0.20	0.40	88%
Sub-Additive 1	0.25	0.25	0.35	85%
Sub-Additive 2	0.30	0.30	0.30	89%
Sub-Additive 3	0.25	0.25	0.25	74%

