Time-until-recovery: An important class of secondary analyses will consider the time-until-recovery based on measurements taken every 4 weeks during the year of follow-up. Specifically, we can define the time-until-recovery as the assessment month in which the subject is first observed to achieve an NRS=0 and RMDQ <= 2. We will use discrete time (monthly data) cumulative incidence curves to show the percent of subjects in each treatment group who have achieved a first recovery by each follow-up time period. We recognize that recovery may not be maintained, and subjects may subsequently relapse so we will also display plots showing the percent of subjects who are currently in the recovered state as a function of time. Formal comparison of cumulative incidence curves can be obtained using the log rank test since in this situation the cumulative incidence is simply 1-survival as would be computed using Kaplan-Meier curves. In addition, we will use a model-based survival analysis.

Cross-sectional outcomes at 2, 6, and 12 months: We will also conduct analysis of change in pain NRS, RMDQ, and STarT Back status from baseline. Satisfaction will also be analyzed at these

time points. This analysis will evaluate the magnitude of short, medium, and long-term effects of treatment, which are traditionally used in systematic reviews and meta-analyses.

Mediation Analysis for Psychosocial Factors: Formal mediation analysis ¹⁵⁵⁻¹⁵⁷ will focus on characterizing the degree to which self-efficacy, coping, kinesiophobia, and pain catastrophizing measured at 8 weeks can explain treatment effects at 6 months, and whether these measures obtained at 6 months explain long-term treatment effects (1 year). We will quantify the percent of the treatment effect that is explained by changes in each scale individually, and in totality when included in a multivariate model for the outcome.¹⁵⁸ We will analyze mediation for cLBP, recovery at six months and change in pain NRS and RMDQ measured at 6 months and 1 year.

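### The derivation rule for the primary pain outcome averages monthly measurements, while the objective and the schedule specify weekly NRS scores; the expected numerical effect is modest

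*Combined protocol and SAP*

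**What the plan says.** - **Objective.** The Précis gives the second research question as "Average pain intensity and low back disability over 1 year as measured by weekly NRS and monthly RMDQ scores". Section 9, under Primary Effectiveness Outcome # 2 and 3, repeats the split by instrument: "based on monthly measures of RMDQ and weekly Pain NRS scores".
- **Derivation.** A few lines later, the paragraph on primary outcome variables applies one rule to both outcomes: "calculating the time-averaged patient outcome using the monthly measurements taken over the year of follow-up".
- **Collection.** Section 3.7: "Individual participants will be followed on a weekly basis for 52 weeks from randomization". Section 6.2.4 lists pain intensity as a primary outcome under weekly follow-up ("The following outcomes will be collected on a weekly basis for one year"). Its monthly list ("Monthly follow-up data (Months 1-12) will be collected electronically via direct patient self-report") names RMDQ and LBP Impact as primary outcomes, not the pain NRS. The table in Section 6.1 marks follow-up pain intensity in the weekly column only. Section 6.2.2 leaves the pain item out of the PROMIS-29 because pain is asked weekly.
- **Elsewhere in Section 9.** The power paragraph for outcomes 2 and 3 speaks of a mean area under the curve and gives no sampling frequency. Of the secondary analyses, the trajectory analysis uses weekly pain and the concomitant-therapy analysis uses monthly pain NRS. The recovery analysis is "time-until-recovery based on measurements taken every 4 weeks during the year of follow-up".

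No section says which weekly score, or what average of weekly scores, would count as a monthly pain measurement.

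**The concern.** A programmer would implement the derivation sentence, and for pain it conflicts with the objective and with the data collected. Average pain is tested at 0.05/2 in a confirmatory global test, so its definition should allow one reading only.

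Two things are at stake. The first is the estimand. The NRS asks about the past week (Section 6.2.2), so a first score at about week 4 carries nothing about weeks 1-3, which fall within the 8-week treatment period. A weekly and a monthly average estimate the same treatment difference if that difference is constant over the year, but not in general otherwise. The second is precision: fewer scores per person give a somewhat noisier average.

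**Working it through.** **1. The plan's own power figures.** Table 9.2 gives 88, 85, 89, 74, 96, 88, 83 and 71%. I used a 3-df F-test at alpha 0.025 with period adjustment. Cell sizes at 90% follow-up were 180 per arm under full randomization, plus 90 each in MC and SSM from the restricted period. Section 9 states the 90% follow-up and the imbalance for LBP Impact; applying them here is an assumption.

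Noncentrality for Sub-Additive 2 (all effects 0.30):
- full randomization: 0.09 × (3 × 180 − (3 × 180)²/720) = 0.09 × 135 = 12.15
- restricted period: 0.09 × (90 − 90²/180) = 0.09 × 45 = 4.05
- total 16.2, power 89.4% against 89% stated

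The eight rows give 89.4, 86.0, 89.4, 72.8, 95.6, 89.4, 83.7 and 72.8%, all within 2 points. The inputs are standardized effects, scaled by the SD of a single measurement. Sampling frequency does not enter, so Table 9.2 is the same under either definition.

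**2. Score counts.** Weekly rule: 52 of 52. Literal calendar-month rule: 12 used, 52 − 12 = 40 not used. Every 4 weeks: 13 used, 39 not used. On both literal readings weeks 1-3 (3/52 = 5.8% of the year) stay out of the average. If monthly means monthly averages of the weekly scores, none is left out.

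**3. Precision.** The documents give no within-person correlation, so ρ = 0.4-0.7 is assumed. Under compound symmetry, variance of a k-score mean ÷ single-score variance = ρ + (1 − ρ)/k.
- ρ = 0.4: 12 scores 0.4 + 0.6/12 = 0.4500; 52 scores 0.4 + 0.6/52 = 0.4115; ratio 1.093
- ρ = 0.7: 12 scores 0.7 + 0.3/12 = 0.7250; 52 scores 0.7 + 0.3/52 = 0.7058; ratio 1.027

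With serially correlated residuals, 1/k is replaced by the mean of φ^|i−j| over all pairs of assessment weeks, where φ is the week-to-week residual correlation (assumed 0.3-0.8). The ratio is 0.4506/0.4212 = 1.070 at ρ = 0.4, φ = 0.3, and 0.7515/0.7475 = 1.005 at ρ = 0.7, φ = 0.8.

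For scale, take the plan's SD of 3.0 and ρ = 0.4. The SD of the average is 3.0 × √0.4500 = 2.01 (12 scores) or 3.0 × √0.4115 = 1.92 (52 scores). Both are well below the 3.0 used for power.

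**4. Effect estimate.** For an assumed effect shape e(t), compare the mean over weeks 1-52 with the mean over weeks 4, 9, 13, 17, 22, 26, 30, 35, 39, 43, 48, 52.

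| Assumed shape | Monthly/weekly ratio |
|---|---|
| Constant | 1.00 |
| Linear rise to week 8, then flat | 1.03 |
| Rise to week 8, then decay, time constant 26 weeks | 0.997 |
| Rise to week 8, then decay, 13 weeks | 0.98 |
| Rise to week 8, then decay, 8 weeks | 0.96 |
| Largest at week 0, decay 26 weeks | 0.398/0.424 = 0.94 |
| Largest at week 0, decay 8 weeks | 0.117/0.144 = 0.81 |
| Largest at week 0, decay 4 weeks | 0.0444/0.0677 = 0.66 |

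**The case against.** The strongest reply is that the derivation sentence was written with RMDQ in mind and loosely extended to pain. It follows directly after an objective that names weekly NRS, and there is no separate monthly pain item for it to refer to. On that view the weekly definition stands. This is plausible, but the text does not settle it: the concomitant-therapy analysis also refers to monthly pain NRS, and the power paragraph gives no frequency.

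The reply does succeed against several stronger inferences.

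- A reader might infer that 40 of 52 scores are discarded and weeks 1-3 go unsampled. The count depends on reading monthly as 12 single scores, which no section states. Weeks 1-3 are sampled in every case, and the trajectory analysis uses the weekly scores.
- A reader might infer that a monthly average captures only 66-81% of the effect. Those ratios need an effect that is largest at week 0 and fades within 4-8 weeks. Treatment starts up to 7 business days after randomization and lasts 8 weeks. To reach the hypothesized 1-point yearly average, such an effect would have to start at 1/0.144 = 6.9 or 1/0.0677 = 14.8 points on a 0-10 scale.
- A reader might infer an open choice once the data are seen. Two statements of the objective name weekly NRS, and Section 3.2 reports that investigators had no access to outcome data. Some latitude remains, but it is limited.

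**Conclusion.** The contradiction is real and concerns the definition of a primary outcome. The derivation sentence, followed literally, departs from the objective in the Précis and Section 9 and from the weekly-only pain schedule, so it should be corrected as a wrong rule.

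The expected numerical effect is modest. The variance of the pain average would be about 3-9% larger under compound symmetry and about 0.5-7% larger with serially correlated residuals, given assumed correlations of 0.4-0.7. The effect estimate would be nearly unchanged (ratio about 0.96-1.03) for effects that build over the treatment period; the change is material only for an effect that is largest at once and fades within weeks. These sizes rest on the assumed correlations and shapes, and on the single-score reading of monthly. A reader might infer that the study's power is at risk, but Table 9.2 does not depend on this choice.

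**What to change.** Replace the derivation sentence in Section 9 with: *Average pain is the time-average (AUC) of the weekly NRS scores over weeks 1-52; average disability is the time-average of the monthly RMDQ scores over months 1-12; baseline enters only as a covariate.*

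Compute the AUC over actual assessment times, so that uneven collection is handled in one stated way. This is needed because Section 8 allows monthly collection, or a minimum of months 2, 6 and 12, for participants who decline the full questionnaires. Section 10.3.3 also stops the weekly and monthly surveys after loss to follow-up, except at months 6 and 12. Say how missed weeks, and records that do not span the year, are treated under the plan's missing-data section.

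Bring the power paragraph and the concomitant-therapy paragraph into line by naming the pain frequency each uses. Date the change before unblinding.

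The cost is a few sentences in Section 9. The weekly scores are already scheduled, and neither the sample size nor Table 9.2 needs revision.

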In consultation with NCCIH program staff and the DSMB in 2022 we have outlined our planned publications for presenting our main results and have revised the primary statistical test that would be used to evaluate differences in mean outcomes across the treatment groups. Specifically, rather than conduct individual tests of SMT alone, SSM alone, and the combination against medical care with adoption of a multiple comparisons correction for three tests we will now use an overall test of equality across the four groups to conduct a single omnibus hypothesis test followed by the estimation of key group comparisons using Fishers least significant difference methods to construct individual nominal 95% confidence intervals with reporting of the induced simultaneous coverage. These methods will be used for primary analysis of the 3 primary effectiveness outcomes : LBP-Impact and pain and disability.

We plan to present principal findings in two key publications. The first publication would focus on average pain and disability over 1-year as the multiple primary outcomes and present recovery at 6-months (previously a primary outcome) as one of the secondary outcomes. A second paper will focus on LBP Impact averaged over months 10-12 as the primary outcome .

Modifications to Statistical Analysis Plan Regarding Primary Outcome

(edited July 2021)

In consultation with the NCCIH program staff and DSMB in the Spring of 2021 we have changed our primary outcome for assessment of treatment impacts on chronicity prevention. Specifically, we have replaced our original NIH Task Force on Research Standards for Chronic LBP (referred to as RTF) dichotomous chronicity measure with the RTF quantitative impact measure. The LBP-Impact outcome measure is a subset of the Promise 29 measures, **which is already being collected at baseline and every month during the follow-up year from the start of the trial**. As a secondary outcome measure, we will compare differences across treatment groups in the distribution of patients with mild, moderate, and severe impact.

Modifications to Statistical Analysis Plan in Response to COVID-19 Impacts

(edited August 2020)

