Our primary analysis will test the global hypothesis that these three treatment comparisons are all null using a multivariate Wald test with 3 degrees of freedom and alpha=0.05. We will then provide individual confidence intervals for each coefficient that compares an intervention group to medical care based on Fishers least significant difference methods which provide individual nominal 95% confidence intervals and also estimates the simultaneous coverage probability.

Power and Sample Size for Primary Outcome of LBP Impact: To characterize the power of our primary analysis (an overall F-test) we provide a summary table that considers potential standardized mean differences comparing the individual intervention arms to medical care. For a small effect size (Cohen's d of 0.2) and an additive effect we have greater than 90% power to reject the null. However, additivity may not hold so we also consider sub-additive scenarios, and the scenario where only one intervention is effective. For small to moderate effect sizes (0.2 – 0.3 standard deviations) we have >90% with our proposed design. We assume n=1000 enrolled with a realistic 90% follow-up that yields 900 evaluated subjects. We also account for the

imbalanced design due to restricted randomization that will yield approximately 300 subjects in the UMC and SSM alone groups and 200 subjects in each of the SMT and SMT+SSM groups. Power is calculated based on 5,000 simulation replications for each scenario and presented in Table 9.1.

The current design is robust to the enrollment target and follow-up assumptions. For example, with an enrollment of n=1000 subjects and 85% follow-up we would have 90% power for our expected alternative scenario with small treatment effects (0.30 standardized mean difference) that are not additive (sub-additive 1).

A secondary evaluation will consider whether the separate effects of SMT and SSM are potentially additive and this will be done using a formal test for interaction:

$$\text{Interaction Model: } E(Y_{ij} \mid X_{ij}) = \beta_0 + \beta_1 \cdot \text{Site}(2)_j + \beta_2 \cdot \text{RiskGroup}_{ij} + \beta_3 \cdot \text{SMT}_{ij} + \beta_4 \cdot \text{SSM}_{ij} + \beta_5 \cdot \text{SMT}_{ij} \cdot \text{SSM}_{ij} + \beta_6 \cdot \text{Period}(2)_{ij} + \beta_7 \cdot \text{Period}(3)_{ij}$$

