Single effect 1a	0	0.30	0.30	96%
Single effect 1b	0.30	0	0.30	88%
Single effect 2a	0	0.25	0.25	83%
Single effect 2b	0.25	0	0.25	71%

Our primary analysis will test the global hypothesis that these three treatment comparisons are all null using a multivariate Wald test with 3 degrees of freedom and alpha=0.05/2 to account for the pair of primary outcomes (pain and disability). We will then provide individual confidence intervals for each coefficient that compares an intervention group to medical care based on Fishers least significant difference methods which provide individual nominal 95% confidence

intervals and also estimates the simultaneous coverage probability.

A secondary evaluation will consider whether the separate effects of SMT and SSM are potentially additive, and this will be done using a formal test for interaction:

$$\text{Interaction Model: } E(Y_{ij} | X_{ij}) = \beta_0 + \beta_1 \cdot \text{Site}(2)_j + \beta_2 \cdot \text{RiskGroup}_{ij} + \beta_3 \cdot \text{SMT}_{ij} + \beta_4 \cdot \text{SSM}_{ij} + \beta_5 \cdot \text{SMT}_{ij} \cdot \text{SSM}_{ij} + \beta_6 \cdot \text{Period}(2)_{ij} + \beta_7 \cdot \text{Period}(3)_{ij}$$

In this model a test of H0: $\beta_5=0$ allows us to determine if there is strong evidence for synergistic or antagonistic effects associated with combined treatment. Given that we evaluate interaction for both disability and pain we will use a Bonferroni corrected alpha of 0.05/2.

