Power and Sample Size for primary effectiveness outcomes # 2 and # 3: See Table 9.2. We will conduct longitudinal analysis of the underlying RMDQ and Pain NRS scores. Specifically, we will conduct analyses using the mean area under the curve for both disability and pain and use linear regression to evaluate treatment effects on the native underlying scales. With n=1000 subjects evaluated through one year and using alpha=0.05/2 for the two outcomes and an overall F-test we have >80% power across a range of scenarios presented in the table below. To orient standardized effects a marginal 2-point mean difference on RMDQ for any treatment modality compared to UMC assuming a standard deviation of 6.5 or less,^{149 153} corresponds to a Cohen's D of $2.0/6.5 = 0.31$, and >80% power to detect a marginal 1-point difference on Pain NRS assuming a standard deviation of 3.0 or less corresponds to a standardized effect of 0.33.^{149 153} Note that our outcome is the area under the curve through 12 months, which is a patient-level weighted average, and the standard deviation (SD) for this outcome will be less than the SD for a single measurement. Our power calculations are conservative since we use the SD for a single measurement. Although we have <80% power if SMT and SSM have small marginal effects of 0.25 SD and no additional benefit when combined (sub-additive 3 below) this scenario leads to no single treatment arm yielding an effect of 2 points on RMDQ (0.31 SD) or 1 point on Pain NRS (0.33 SD) and therefore suggests our design is appropriate for important and plausible effect sizes and not overpowered for effects that may not be meaningful.

Furthermore, we have excellent power to detect interaction effects where the effect of SMT and SSM may be synergistic or antagonistic, and using alpha=0.05/2 we have >80% to detect a 2.7-point difference in disability or 1.3-point difference in pain treatment effects of one modality across the strata defined by the other treatment modality.

Secondary Analyses of the 3 primary effectiveness outcomes and other secondary outcomes: We will conduct a number of pre-specified secondary analyses.

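### Pain and disability (and their interaction tests) are held at a fixed 0.05/2; Holm's step-down rule gives the same 0.05 control of each pair and never rejects less (an efficiency gain, not an error)

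*Combined protocol and SAP*

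**What the plan says.** All references are to section 9 of the combined protocol and SAP.

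- **Omnibus tests, Primary Effectiveness Outcomes #2 and #3.** For each outcome the plan tests that the three contrasts with medical care (MC) are all zero, "using a multivariate Wald test with 3 degrees of freedom and alpha=0.05/2 to account for the pair of primary outcomes (pain and disability"). Table 9.2 gives power at that level.
- **Interaction tests, same outcomes.** For the SMT-by-SSM term, "we will use a Bonferroni corrected alpha of 0.05/2". The power text adds that "using alpha=0.05/2 we have >80% to detect a 2.7-point difference in disability or 1.3-point difference in pain treatment effects".
- **LBP Impact.** This third primary outcome has its own omnibus test, "using a multivariate Wald test with 3 degrees of freedom and alpha=0.05. We will then provide individual confidence intervals".
- **Role of the pair.** The multiplicity modification plans one paper with "average pain and disability over 1-year as the multiple primary outcomes" and a second on LBP Impact. Nowhere is success required on both pain and disability.
- **Variance.** The power text states: "Our power calculations are conservative since we use the SD for a single measurement". The primary analysis adds: "We will also add the baseline outcome as a covariate".

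No step-down or alpha-recycling rule appears for either pair.

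**The concern.** A fixed split spends 0.025 on each hypothesis whatever happens to the other. Once one null of a pair has been rejected, only one hypothesis is left that could be falsely rejected, and it can be tested at 0.05 without the pair's familywise error exceeding 0.05. Under the present rule, if disability is clearly rejected and pain gives p = 0.03, pain is declared non-significant although the pair's error budget would have allowed rejection.

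Pain and disability carry separate hypotheses in the plan, so the second rejection is a result in its own right. What is at stake is the power to claim it. Neither the validity of the trial nor the chance of a first positive finding is affected.

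**Working it through.** **1. Why the error control is the same.** With Holm, if both nulls are true, any false rejection needs the smaller p-value to be at most 0.025, which has probability at most 0.025 + 0.025 = 0.05. If one null is true, rejecting it needs its own p-value to be at most 0.05. No correlation assumption is used. The first step is identical to the fixed split, so Holm rejects everything the fixed split rejects, and the chance of at least one rejection is the same.

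**2. Inputs.** 1000 enrolled, about 300 in MC and in SSM and 200 in SMT and in SMT+SSM, with 90% follow-up (LBP Impact power text). I read this as 180 evaluated per arm in the full-factorial periods plus 90 MC and 90 SSM in the restricted period. SDs are 6.5 (RMDQ) and 3.0 (NRS); targets are 2 and 1 points.

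**3. Reproducing Table 9.2.** With period indicators in the model, the information for the contrasts (SMT, SSM, SMT+SSM against MC), in SD units, is the sum over periods of diag(n) − nn′/N:

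- diagonal: SMT 180 − 180²/720 = 135; SSM 135 + (90 − 90²/180) = 180; SMT+SSM 135
- off-diagonal: −180²/720 = −45

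The standard errors are 0.101, 0.086 and 0.101. Noncentrality is λ = d′Vd. For 0.25 in all arms, λ = 0.0625 × (135 + 180 + 135 − 6 × 45) = 0.0625 × 180 = 11.25. Power is the noncentral chi-square (3 df) tail beyond the 0.025 critical value.

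| Scenario | λ | Recomputed | Table 9.2 |
|---|---|---|---|
| Additive | 16.20 | 89.5% | 88% |
| Sub-Additive 1 | 14.85 | 86.2% | 85% |
| Sub-Additive 2 | 16.20 | 89.5% | 89% |
| Sub-Additive 3 | 11.25 | 73.0% | 74% |
| Single 1a | 20.25 | 95.7% | 96% |
| Single 1b | 16.20 | 89.5% | 88% |
| Single 2a | 14.06 | 83.9% | 83% |
| Single 2b | 11.25 | 73.0% | 71% |

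All eight agree within 2 points.

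**4. Fixed split against Holm.** 400,000 draws of the contrasts for two outcomes with correlation 0.5-0.7 (assumed), applying both rules to the same draws. Target effects are 2/6.5 = 0.31 SD and 1/3 = 0.33 SD in every active arm. SD ratio means the SD of the averaged outcome divided by that of a single measurement.

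| Scenario | SD ratio | Quantity | Fixed | Holm |
|---|---|---|---|---|
| Targets | 1.0 | disability | 91% | 94% |
| Targets | 1.0 | pain | 95% | 97% |
| Targets | 1.0 | both | 88-89% | 93% |
| Targets | 0.9 | both | 95-96% | 97% |
| Targets | 0.8 | both | 98.9% | 99.5% |
| Sub-Additive 2 | 1.0 | both | 82-84% | 89% |
| Sub-Additive 3 | 1.0 | each | 73% | 78% |
| Sub-Additive 3 | 1.0 | both | 59-62% | 69-72% |
| Sub-Additive 3 | 0.9 | both | 73-75% | 81-83% |
| Sub-Additive 3 | 0.8 | both | 87-88% | 92% |
| Sub-Additive 3 | 0.7 | both | 96% | 98% |

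The documents do not give the SD ratio. For a mean of 12 monthly scores with within-patient correlation r it is √((1 + 11r)/12) before baseline adjustment, so 0.9, 0.8 and 0.7 correspond to r = 0.79, 0.61 and 0.44.

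**5. Interaction tests.** The SE is √(1/270 + 1/270 + 1/180 + 1/180) = 0.136 SD. The stated effects are 2.7/6.5 = 0.415 SD and 1.3/3.0 = 0.433 SD. Power at 0.025 is 79% (disability) and 83% (pain) with 900 evaluated, and 84% and 87% with 1000, against the stated figure of more than 80%. If both interactions are present, power to reject both goes from 70-72% to 79-80% at unit SD, and from 91-92% to 95% at ratio 0.8.

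**6. What Holm costs in error.**

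| Situation | Fixed | Holm |
|---|---|---|
| Both of the pair null: any false omnibus rejection | 4.3-4.7% | 4.3-4.7% |
| One responds at 0.30 SD in all arms: false rejection of the other | 2.5% | 4.6-4.7% |
| Same: any false 95% interval for the null outcome after its omnibus rejection | 2.2% | 3.8-3.9% |
| Same, LBP Impact also null: any false omnibus rejection over three primaries | 6.6-7.0% | 8.2-8.9% |
| All three null | 7.9-8.9% | 7.9-8.9% |

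The bound over all three primaries is 0.05 + 0.05 = 0.10 under either rule.

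**The case against.** The strongest case for leaving the plan alone is that nothing in it is wrong. The split is pre-specified, valid and matched to the power table, and it keeps each outcome's verdict independent of the other's p-value, which suits analyses described as parallel.

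The gain is also small where the plan expects its effects to lie. If the combined arm does 1.3 times as well as a single arm (assumed), both-outcome power at unit SD goes only from 95% to 97%. The largest gains arise in Sub-Additive 3, which the plan itself places below a meaningful effect. They also use an SD that the plan says overstates the variance. Finally, multiplicity was the concern that the NIH statistician raised in 2021, and Holm raises the error on a null outcome when the other responds.

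The points on size stand: the unit-SD figures are upper-end, and the benefit at the targets runs from about 5 points down to less than 1. The interaction pair is only a secondary evaluation. The error point stands as a fact but is a weak reason to decline, because the increase stays inside the 0.05 already allotted to the pair. Nor is a matching confidence interval given up, since the plan's intervals after the omnibus test are nominal 95%, not 97.5%.

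**Conclusion.** The point holds as an efficiency improvement; the current rule is not an error, and no change in sample size follows from it. That Holm gives the same 0.05 control of each pair and never rejects less rests on no assumption. The size of the gain does rest on assumptions: 900 evaluated, outcome correlation 0.5-0.7, and equal standardized effects on both outcomes except at the plan's targets. On those terms, at unit SD, per-outcome omnibus power rises by about 1-5 points and power to reject both by about 3-10 points. The gain is modest at the target effects, larger below them, and smaller throughout as the averaged outcome's SD falls. It is worth making because it costs almost nothing.

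**What to change.** In the primary analysis of outcomes #2 and #3, replace the fixed level with this rule: test the smaller of the pain and disability omnibus p-values at 0.025 and, if it is rejected, test the larger at 0.05. Apply the same rule to the two interaction p-values. Keep Table 9.2 and describe it as minimum per-outcome power. State that the 0.05 control covers the pain-disability pair only and that LBP Impact keeps its separate 0.05.

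The cost is a wording change before unblinding, with no added patients or data. The last multiplicity revision was made "In consultation with NCCIH program staff and the DSMB in 2022", so this change should take the same route, with the error rates in step 6 disclosed. If the sponsor prefers the fixed split so that each outcome's verdict stands alone, one sentence giving that reason would settle the matter.
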